#### 4.2.3    Multiple Imputation

A multiple imputation will be performed based on MAR for AIN457 6mg/kg - 3mg/kg for baseline weight, baseline and post-baseline of each parameter for visits up to the primary time point (e.g Week 52) using Markov Chain Monte Carlo (MCMC) method with EM algorithm.

Impute the missing values 100 times (NIMPUTE) with a seed=457<studycode> as shown below:

```
proc mi data= out=imp minmaxiter=10000000 nimpute=100 seed=4572302;
```

```
    by trt;
```

```
    var weight_base strata var1_base var1_week1-var1_week52;
```

```
    mcmc chain=multiple initial=em;
```

```
run;
```

If needed repeat for each component necessary to calculate the final score, e.g. as follows:

```
proc mi data=imp out=imp2 minmaxiter=10000000 nimpute=100 seed=4572302;
```

```
    by trt _imputation_;
```

```
    var weight_base strata var2_base var2_week1-var2_week52;
```

```
    mcmc chain=multiple initial=em;
```

```
run;
```

Post-processing of out of range imputed values will be processed with the min and max values of each variable.

The score and ACR response can now be calculated based on the complete data. The response rate will be calculated for each imputation and then combined using Rubin's rules.

In order to calculate the response rate for each imputation, PROC FREQ will be used as follows.

Calculate binomial proportion and standard error for each imputation.

```
proc freq data=<ACR20>;
  by treat visit _imputation_;
  tables <response> / binomial (level=2 cl=wilson correct);
  ods output BinomialProp=imp_bpr;
run;
```

Transpose the dataset for subsequent use with PROC MIANALYZE.

```
proc transpose data=imp_bpr out=imp_trs(drop=_name_);
  by treat visit _imputation_;
  var nvalue1; id name1; idlabel label1;
run;
```

Apply LOGIT transformation:  $y=\log(p/(1-p))$  and std. err. transformation: <new se> =  $se/(p*(1-p))$

```
data logit;
  set imp_trs(rename=(_bin_=p e_bin=se));
  by treat visit _imputation_;
  lmean=log(p/(1-p));
  lse=se/(p*(1-p));
run;
```

The transformed binomial proportion estimates and standard errors are combined by applying Rubin's rules for multiple imputed data sets.

```
proc mianalyze data=logit;
  by treat visit ;
  modeleffects lmean;
  stderr lse;
  ods output ParameterEstimates=logitres;
run;
```

The combined data should be transformed back using the following formula:  $p=1/(1+\exp(-y))$

```
data miexpress;
  set logitres;
  by treat visit ;
  resti = 1/(1+exp(-estimate));
```

```
rlow = 1/(1+exp(-lclmean));  
rupp = 1/(1+exp(-uclmean));  
run;
```

Of note, sometimes all responses may be imputed to 0 or 1 at a given combination of response variable, treatment group and visit. Such cases should be considered separately. The combined final response rate would be the same as the original response but the 95% CI will be undefined.

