12.4.3 Handling of missing values/censoring/discontinuations

Missing data for ACR50 response and other binary efficacy variables (e.g. ACR20, [REDACTED] HAQ-DI[®] response, etc.) for data up to Week 16 will be handled as follows:

- Subjects who drop out of the trial for any reason will be considered non-responders from the time they drop out through Week 16 based on the estimands.
- Subjects who do not have the required data to compute ACR response (i.e. tender and swollen joint counts and at least three of the five ACR core set variables) at BSL and at the specific time point will be classified as non-responders.

Continuous variables (e.g. [REDACTED], [REDACTED], etc.) will be analyzed using a mixed-effects repeated measures model (MMRM) which is valid under the missing at random (MAR) assumption. For analyses of these parameters, if all post-BSL values are missing then these missing values will not be imputed and this subject will be removed from the analysis of the corresponding variable, i.e. it might be that the number of subjects providing data to an analysis is smaller than the number of subjects in the FAS.

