### **2.5 Efficacy Evaluation**

#### **2.5.1 Description of Efficacy Variables**

##### **ACR 20/50/70**

The ACR response will be used to determine efficacy. A subject is defined as an ACR 50 responder if, and only if, the following three conditions hold:

≥ 50% improvement in the number of tender joints (based on 78 joints)

≥ 50% improvement in the number of swollen joints (based on 76 joints)

≥ 50% improvement in three of the following five measures:

Patient's global assessment of disease activity (measured on a VAS scale, 0-100)

Physician's global assessment of disease activity (measured on a VAS scale, 0-100)

Patient's assessment of PsA pain (measured on a VAS scale, 0-100)

Health Assessment Questionnaire- Disability Index (HAQ-DI©) score

Acute phase reactant (hsCRP or ESR)

ACR20 = 20 % improvement in at least 3 of the 5 measures and 20 % improvement in the swollen and tender joint count.

ACR50 = 50 % improvement in at least 3 of the 5 measures and 50 % improvement in the swollen and tender joint count.

ACRn =  $\min (x_1, x_2, x_3)$ , where

$x_1$  = % improvement from baseline in tender 78-joint count

$x_2$  = % improvement from baseline in swollen 76-joint count

and  $x_3$  = 3rd largest value of  $x_4, x_5, x_6, x_7, x_8$  where,

$x_4$  = % improvement from baseline in Patient's assessment of PsA pain (VAS 100 mm)

$x_5$  = % improvement from baseline in Patient's global assessment of disease activity (VAS 100 mm)

$x_6$  = % improvement from baseline in Physician's global assessment of PsA disease activity (VAS 100 mm)

$x_7$  = % improvement from baseline in Patient self-assessed disability (Health Assessment Questionnaire [HAQ®] score)

$x_8$  = % improvement from baseline in Acute phase reactant (C-reactive protein [hsCRP]) or Erythrocyte sedimentation rate (ESR)

ACRn can be computed even if up to two values of  $x_4, x_5, x_6, x_7, x_8$  are missing. ACRn, theoretically, cannot be computed, if one or both of  $x_1, x_2$  is/are missing OR more than three values of  $x_4, x_5, x_6, x_7, x_8$  are missing.

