#### Missing data

Missing data for primary and key secondary binary efficacy variables for data up to Week 52 will be handled as follows:

- Subjects who drop out of the trial for any reason will be considered non-responders from the time they drop out through Week 52 for active groups or through Week 16 for placebo group.
- Subjects who do not have the required data at baseline and at the specific time point to compute response will be classified as non-responders.

Data collected after Week 16 will generally be presented as 'observed case'; i.e. all available data for each time point will be included in the analyses. In addition, multiple imputation will be used for ACR50. These will be presented for AIN457 6mg/kg - 3mg/kg treatment group only. Observed data summary will be presented by treatment sequence ([Section 2.2.2](#)).

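### SAP 4.2.3 sets nimpute=100 again in the second PROC MI call, so the two printed calls give 10,000 copies per subject rather than the stated 100

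*SAP*

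**What the plan says.** SAP 2.5.3 presents data after Week 16 mainly as observed cases and adds an imputed summary for one endpoint in one arm: "In addition, multiple imputation will be used for ACR50. These will be presented for AIN457 6mg/kg - 3mg/kg treatment group only".

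SAP 4.2.3 describes the method. The text sets the number of imputations at 100, and the first PROC MI call uses `nimpute=100` by treatment and writes the file `imp`. The SAP then continues: "If needed repeat for each component necessary to calculate the final score, e.g. as follows". The example that follows is "proc mi data=imp out=imp2 minmaxiter=10000000 nimpute=100 seed=4572302", run `by trt _imputation_`.

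After imputation, ACR response is derived on the completed data, and "The response rate will be calculated for each imputation and then combined using Rubin's rules". The code does this with PROC FREQ by treatment, visit and `_imputation_`, followed by PROC MIANALYZE. No step between the imputation calls and PROC FREQ reduces the number of copies or gives them a new index.

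ACR50 is a multi-component score. SAP 2.5.1 requires 50% improvement in both joint counts and "improvement in three of the following five measures".

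**The concern.** PROC MI applies `nimpute` within each BY group. The second call treats each of the 100 completed files as a BY group, so it makes 100 new copies of each one. The code then disagrees with the stated count of 100. ACR50 has several components, so the example that carries the error is the one a programmer would repeat.

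Two things are at stake. A long chain of such calls would not finish, and the repair would be improvised outside the prespecified plan. A short chain would run, but could feed repeated copies of the same patient into PROC FREQ as if they were different patients. That gives a confidence interval that is too narrow, possibly with nothing to signal the problem.

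**Working it through.** **Inputs**

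- Imputations intended, and `nimpute` in both printed calls: 100 (SAP 4.2.3).
- Subjects in the imputed arm: about 190 (SAP 1.1).
- ACR50 components, maximum: 2 joint counts + 5 measures = 7 (SAP 2.5.1).
- ACR50 components, minimum: Protocol 12.4.3 needs "tender and swollen joint counts and at least three of the five ACR core set variables", so 2 + 3 = 5. The SAP agrees in saying that "ACRn can be computed even if up to two values of" the five measures are missing.

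**Copies per subject.** After k calls, each reading the previous output by imputation number, copies = 100^k and rows = 190 x 100^k.

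| Calls (k) | Copies per subject | Rows for 190 subjects | Status |
|---|---|---|---|
| 1 | 100 | 19,000 | matches the stated 100 |
| 2 | 10^4 | 1.9 million | the calls as printed |
| 5 | 10^10 | 1.9 x 10^12 | assumes chaining, minimum components |
| 7 | 10^14 | 1.9 x 10^16 | assumes chaining, all components |

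If every later call instead read `imp` again, each would give 10^4 copies. That is still not 100, but it would never reach 10^10.

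**Feasibility of the chained case.** At an assumed 8 bytes per value, one variable takes 1.9 x 10^12 x 8 = 1.52 x 10^13 bytes (about 15 TB) for five components. For seven it takes 1.9 x 10^16 x 8 = 1.52 x 10^17 bytes (about 152 PB).

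**Effect on the standard error with two calls.** Assume the 10^4 copies end up under 100 values of `_imputation_`. Each PROC FREQ cell then holds 10^4 / 100 = 100 copies of each patient, so 190 patients are counted as 19,000. At a response rate of 39.6% (the 300 mg s.c. Week 16 rate in SAP 3.1.1, used only as an illustration):

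- correct: sqrt(0.396 x 0.604 / 190) = 0.0355, or 3.55 points;
- with repeated copies: sqrt(0.396 x 0.604 / 19,000) = 0.00355, or 0.355 points.

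The within-imputation standard error is 10 times too small. The pooled interval also depends on the between-imputation variance, which the documents do not give, so its exact narrowing cannot be computed.

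**Effect on the rate.** Every patient is copied the same number of times, so patients keep equal weight and the response rate is not biased.

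**After the correction.** With `nimpute=1` in later calls, copies = 100 x 1^(k-1) = 100, and rows = 190 x 100 = 19,000 for any k.

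**The case against.** The best defence is that this is template code. The first call names no input file, the PROC FREQ step has an ACR20 placeholder although the endpoint is ACR50, and the variable list starts at Week 1 although the first post-baseline window in SAP Table 4-1 is Week 4. A programmer must adapt it anyway, and the text around it (100 imputations, one rate per imputation, Rubin's rules) is sound. The repeat is also conditional and given as an example. A run that exploded would fail visibly and report no wrong number.

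Much of this stands, and it is why the point is minor. It does not remove the contradiction. The wrong value sits in the line meant to be repeated, and the SAP shows no other way to impute several components. Nor is the repeat unlikely to be needed. Protocol Section 5 expects 10% dropout after randomization, and a subject who is no longer assessed has every component missing at later visits.

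A reader might infer that the plan as written produces 10^10 to 10^14 copies and so cannot be run. The documents do not go that far. Only two calls are printed, and they give 10^4 copies, which can be run. The larger figures need each call to read the last one's output and one call per component. The sources for five to seven components say what an ACR response requires, not how many PROC MI calls to make.

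**Conclusion.** The point holds in limited form, with low severity. The printed code gives 10^4 copies per subject against the stated 100, and nothing afterwards restores 100. This follows from the SAP's own text and needs no assumption beyond `nimpute` acting within BY groups.

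Two further consequences are conditional. The infeasible 10^10 to 10^14 copies assume chained calls, one per component. The tenfold shortfall in the within-imputation standard error assumes that fewer calls are used, that the copies are not renumbered, and that the software leaves 100 index values. The documents do not state how the output is numbered.

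It would be wrong to infer that ACR50 estimates are biased or that the primary result is in doubt. The affected output is a descriptive long-term rate in one arm, shown in addition to observed-case results. SAP Section 1 says that Week 16 analyses and those in the testing hierarchy are not repeated at this database lock.

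**What to change.** In SAP 4.2.3:

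1. Keep `nimpute=100` in the first PROC MI call only.
2. Set `nimpute=1` in every later call. Before each one, copy `_imputation_` to a separate variable (for example `imp_no`), run by treatment and `imp_no`, and restore it as `_imputation_` afterwards. This works however the software numbers its output.
3. State that each later call reads the output of the previous one.
4. Before PROC FREQ, check that there are exactly 100 index values and one record per patient in each treatment, visit and imputation cell.

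Standard Rubin's rules then apply to 100 completed data sets, as the text intends. The cost is a few characters of example code, one copy-and-restore step per further component and one record-count check. Computing time falls.

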#### 4.2.4 Crude incidence and relativ risk estimates

##### 4.2.4.1 Odds ratio and 100\*(1- $\alpha$ )% confidence interval

For an investigational drug group with  $n_1$  subjects at risk, independent from the control group (e.g. placebo or comparator) with  $n_0$  subjects at risk, of whom  $x_1$  and  $x_0$  experience a certain event with probability  $\pi_1$  and  $\pi_0$  respectively, the odds ratio is estimated as

$$\frac{p_1/(1-p_1)}{p_0/(1-p_0)}$$
 with  $p_1=x_1/n_1$  and  $p_0=x_0/n_0$ . A conditional exact 100\*(1- $\alpha$ )% confidence interval will be obtained by using the SAS procedure PROC FREQ with statement EXACT OR.

#### 4.2.5 Exposure adjusted incidence rate and related risk estimates

##### 4.2.5.1 Exposure adjusted incidence rate and 100\*(1- $\alpha$ )% confidence interval

It will be assumed that for each of  $n$  subjects in a clinical trial the time  $t_j$  ( $j=1, \dots, n$ ) to the first occurrence of a certain event is observed, or if the event was not experienced, the (censored) time to the end of the observation period. The sequence of first occurrences of an event will be modeled to follow approximately a Poisson process with constant intensity  $\theta$ . The rate

parameter  $\theta$  will be estimated as  $\lambda=D/T$ , where  $T = \sum_{j=1}^n t_j$  and  $D$  is the number of subjects with

at least one event. Conditionally on  $T$ , an exact 100\*(1- $\alpha$ )% confidence interval for a Poisson variable with parameter  $\theta T$  and observed value  $D$  can be obtained based on (Garwood, 1936), from which an exact 100\*(1- $\alpha$ )% confidence interval for  $D/T$  will be derived as follows (Sahai, 1993; Ulm, 1990):

$$\text{Lower confidence limit } L = \frac{0.5c_{\alpha/2,2D}}{T} \text{ for } D>0, 0 \text{ otherwise,}$$

$$\text{Upper confidence limit } U = \frac{0.5c_{1-\alpha/2,2D+2}}{T}$$

where  $c_{\alpha,k}$  is the  $\alpha$ th quantile of the Chi-square distribution with  $k$  degrees of freedom.

The example below shows how this should be handled for cases where subjects switch treatment. In particular for summarizing 'Any secukinumab' as a group, one should take into consideration the sequence of treatments while calculating exposure time for subjects.

**Table 4-3 Examples for calculating exposure time for incidence rates (IR)**

1st treatment	1st exposure	2nd treatment	2nd exposure	Event days (in terms of study day)	Exposure for IR
Placebo	100 days	150 mg	200 days	50 (1st trt) 110 (10 days into 2nd trt)	Placebo: 50 days (event) 150 mg: 10 days (event) Any AIN: 10 days (event)

